13.1.2.1 Primary Objectives

- To determine the response rate of the combination of trametinib and navitoclax in subjects with KRAS or NRAS mutation-positive advanced or metastatic solid tumors in disease-specific expansion cohorts.
- To confirm the safety and tolerability of trametinib and navitoclax in combination at the RP2D determined in the Phase 1b portion.

13.1.2.2 Primary Endpoints

- Response rate (partial response [PR] + complete response [CR])
- Progression-free survival (PFS)
- Adverse events

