2.4 Rationale

Previously, our laboratory and others showed that simultaneous targeting of more than one RAS effector pathway (specifically the MEK-ERK (MAPK) and PI3K-AKT pathways) caused marked responses in KRAS-driven mouse tumor models (Engelman et al., 2008; She et al., 2010). While these data support the promise of combination therapy strategies, toxicity has prevented dosing both medications at or near their maximally-tolerated doses when used in combination (LoRusso et al., 2012; Bedard et al., 2012; Speranza et al., 2012). Thus, potent and continuous suppression of the MEK and PI3K pathways may not be possible in patients with currently available agents. Furthermore, this approach may be effective only in a subset or KRAS-mutant cancers. Consequently, additional effective combination therapy strategies for KRAS-mutant cancers are critically needed.

A large-scale screening study of >600 cell lines with >100 targeted compounds identified MEK inhibitors as the most effective agents in KRAS-mutant cell lines (Garnett et al., 2012). However, while MEK inhibition alone leads to decreased proliferation in most KRAS mutant cancers, MEK inhibitors alone typically fail to induce a cell death response ([name] et al., 2013). This observation likely explains why MEK inhibitors have often led to stable disease in KRAS-mutant cancer patients (Infante et al., 2010), but have rarely, if ever, led to true objective tumor responses. Still, because of their potent growth inhibitory effects and their ability to cause disease stabilization in patients with KRAS mutant cancers, MEK inhibitors are a promising backbone for potential combination strategies for KRAS mutant cancers.

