11.1.6 Progression-Free Survival

PFS is defined as the duration of time from start of treatment to time of progression or death, whichever occurs first.

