13.1.2 Part 2 (Phase 2)

Part 2 is a single-arm Phase 2 study of trametinib in combination with navitoclax at the RP2D determined in the Phase 1b trial above. Patients with KRAS or NRAS mutation-positive solid tumors will be enrolled into up to 4 different disease-specific expansion cohorts. These will include expansion cohorts for patients with KRAS or NRAS mutation-positive: (1) Pancreatic cancer, (2) GYN cancer, (3) lung cancer, (4) all other solid tumor types exclusive of pancreatic, GYN, and lung cancers. Part 2 aims to evaluate the efficacy of this regimen in the tumor types above and to further evaluate the safety and toxicity profile of this regimen at the RP2D defined in Part 1 of the study. Paired pre-treatment and on-treatment (day 15) tumor biopsies will be obtained on the first 15 patients enrolled in Part 2 (minimum 4 patients biopsied in each of expansion cohorts 1, 2, and 3) to assess the pharmacodynamic response to therapy. Adverse events will be reported as defined in Section 7. Evaluation of response rate will be performed as defined in Section 11. PFS will be determined as defined in Section 11.1.6.

NCI Protocol #: 9525

Version Date: July 22, 2022

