The primary goal of Part 2 is to evaluate the efficacy of this regimen in patients with various KRAS or NRAS mutation-positive solid tumor. Based on traditional response rates to standard second line chemotherapy in the tumor types being studied (Guglielmi et al, 2007; Conroy et al, 2011), we conclude that a response rate of 15-20% or greater in a given expansion cohort would deem this regimen worthy of further study in that specific patient population. In part 2, patients will be enrolled in 4 expansion cohorts by a two-stage design, as outlined in Section 5.1. Initially 12 patients will be enrolled to each cohort in Stage 1. If no responses are observed in a given cohort among the first 12 patients, then that cohort will be stopped for futility. However, if one or more responses are observed in a given cohort, the cohort will proceed to Stage 2, and an additional 13 patients will be enrolled for a total of 25 patients in that cohort. If at least three responses are observed within a completed cohort of 25 patients, the regimen will be considered promising for treating the specific tumor type. This design has a 11% false-positive and a 22% false-negative error rate for testing a 17% vs. a 5% response rate. The probability of early stopping is 54% if the underlying response rate were truly only 5%. In the event that the number of responses observed in a given cohort does not meet the pre-established response criteria defined above, but promising anti-tumor activity is observed (such as prolonged stable disease or tumor regressions that fall short of the RECIST cutoff for partial response), the possibility of further evaluating of this regimen in the specific patient population can be explored through a joint discussion between the investigators, pharmaceutical collaborators, and the NCI-CTEP.

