13.1.2.3 Secondary Objective

• To evaluate the pharmacodynamic response to therapy in tumor biopsies (first 15 patients enrolled overall, minimum 4 patients biopsied in each of expansion cohorts 1, 2, and 3)

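### Does listing PFS as a Part 2 primary endpoint, with no objective, benchmark or censoring rule behind it, call for a change to the plan?

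*Combined protocol and SAP*

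**What the plan says.** For Part 2, Section 13.1.2.2 gives three primary endpoints: response rate, "Progression-free survival (PFS") and adverse events. The first primary objective in Section 13.1.2.1 begins "To determine the response rate of the combination of trametinib and navitoclax in subjects with KRAS or NRAS", and the second concerns safety and tolerability. Section 1.1.2 matches. The only secondary objective (Sections 1.1.4 and 13.1.2.3) is "To evaluate the pharmacodynamic response to therapy in tumor biopsies". PFS appears in none of these.

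PFS is nevertheless intended and defined. Section 13.1.2 states "PFS will be determined as defined in Section 11.1.6", and Section 11.1.6 reads "PFS is defined as the duration of time from start of treatment to time of progression or death, whichever occurs first". Section 2.5.3 plans to correlate mutations and biomarkers with response or PFS. Section 13.4 covers secondary endpoints only, and Section 13.5 covers toxicity and response only, so no PFS summary method or censoring rule is written down.

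The decision rule in Section 13.1.2 uses response: stop a cohort at 0 of 12, otherwise enrol 13 more, and call the regimen promising at 3 or more of 25. Its properties are given as "This design has a 11% false-positive and a 22% false-negative error rate for testing a 17% vs. a 5% response rate", with 54% early stopping at a 5% rate. If a cohort misses these criteria but "promising anti-tumor activity is observed (such as prolonged stable disease or tumor regressions that fall short of the RECIST cutoff for partial response"), the parties may jointly discuss whether to evaluate the regimen further in that population.

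**The concern.** A primary endpoint normally has an objective, a summary measure, a reference value and rules for incomplete follow-up. PFS here has only its definition. Follow-up after removal from study is tied to toxicity, with a 30-day minimum (Section 5.5), so some patients may leave without documented progression. Section 13.5.2 counts categories 4-9, including unknown, as treatment failure, and says their precise definitions will be protocol specific, but none is supplied. Two analysts could therefore report different PFS medians.

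The discussion clause seems to compound this. Section 2.4 says that "MEK inhibitors have often led to stable disease in KRAS-mutant cancer patients", and Section 2.2.1.2 reports 11 cases of stable disease among 26 evaluable pancreatic patients on trametinib alone. If disease control of unspecified length can rescue a cohort that failed on response, single-agent behaviour might be read as activity of the combination, and the stated false-positive rate would then understate the real one.

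**Working it through.** **1. Do the stated error rates depend on PFS?** Inputs from Section 13.1.2: 12 patients then 13 more; stop at 0 of 12; success at 3 or more of 25; response rates 5% and 17%.

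- Early stopping at 5%: 0.95^12 = 0.540 (stated 54%).
- P(success) = sum over x = 1 to 12 of P(X = x of 12) × P(at least 3 − x of 13).
- At 5%: 0.3413 × 0.1354 + 0.0988 × 0.4867 + 0.0196 = 0.114 (stated 11%).
- At 17%: 0.2627 × 0.6751 + 0.2960 × 0.9113 + 0.3344 = 0.781, so the false-negative rate is 0.219 (stated 22%).

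All three figures reproduce from response alone. PFS enters none of them.

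**2. How often could the discussion clause apply?** At 5%, P(miss) = 1 − 0.114 = 0.886, made up of 0.540 at Stage 1 and 0.346 at 25 patients. At 17% it is 0.219. If all four cohorts were inactive, 4 × 0.886 = 3.5 would miss. This is only an upper bound on use of the clause, which also requires promising activity and then merely permits a discussion. The plan gives no probability for that second condition, so no inflated error rate can be derived from it.

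**3. Does the stable-disease background show that the clause would be met by default?** With single-agent rates from the documents and n = 12:

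| Source | Rate | Expected of 12 | P(at least 3 of 12) |
|---|---|---|---|
| Trametinib, pancreatic, evaluable patients | 11/26 = 42% | 5.1 | 94% |
| Navitoclax, SCLC, all patients | 9/39 = 23% | 2.8 | 55% |
| Navitoclax, SCLC, evaluable (39 − 13 = 26) | 9/26 = 35% | 4.2 | 84% |

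These are rates of stable disease of any duration, whereas the clause says prolonged. Changing only the denominator moves the navitoclax result from 55% to 84%. The SCLC trial was also not selected for KRAS or NRAS mutation. The table shows that stable disease is common on one drug; it does not measure the clause.

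A landmark calculation fares no better. Take week 24 (5.52 months) and exponential PFS with medians of 1.5 (navitoclax alone in SCLC), 2 or 3 months (both assumed). The progression-free proportions 2^(−5.52/median) are 0.078, 0.148 and 0.279. Keeping the false-positive probability at or below 10% then needs 3, 4 or 6 of 12 patients (tails 0.061, 0.088, 0.088). The landmark, the exponential shape and two of the three medians are not in the plan, so the thresholds follow mainly from assumptions.

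**4. How far could the missing rule for unassessable patients move a PFS median?** Take a cohort of 25 with k patients lacking a post-baseline scan and everyone else followed to progression. Counted as events on day 1, they put the median at observed progression 13 − k. Censored on day 1, they put it at the next whole number at or above (25 − k)/2.

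| k | As events | Censored |
|---|---|---|
| 2 (assumed) | 11th | 12th |
| 4 (assumed) | 9th | 11th |
| 8 (from 25 × 13/39 = 8.3) | 5th | 9th |

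The last row borrows the 13 of 39 patients not evaluable for response in the SCLC trial. Any of those who died would already be PFS events under Section 11.1.6, and Section 11.1.4.3 asks that progression be sought even after treatment stops. The row is therefore an extreme case. No decision rule uses this median.

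**The case for a change.** The best case for a change is that an endpoint labelled primary should carry its own analysis rule, that the correction is only wording, and that a discretionary clause without a threshold invites a favourable reading of the disease control a MEK inhibitor gives by itself. The factual part stands: no PFS objective, benchmark, summary method or censoring rule is given, the definitions promised in Section 13.5.2 are absent, and the word prolonged has no duration.

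The consequences drawn from it do not stand. The PFS event is defined. Stable disease and its duration are defined too (Sections 11.1.4.1 and 11.1.5). The clause neither reopens a cohort nor alters the threshold of 3 in 25, and it names stable disease rather than PFS, so moving PFS to another list would leave it untouched. The inability to separate the combination from trametinib on disease control belongs to any single-arm cohort. A numeric bar for a non-binding discussion would need a reference rate that the documents do not supply for these populations. A sensitivity analysis counting every exit as an event is a matter of preference.

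**Conclusion.** No change follows. The mismatch between endpoints and objectives is a labelling slip: PFS has no hypothesis, error rate or decision attached, so whether it is called primary or secondary alters no result. The missing method is a gap that analysts fill sensibly, using Kaplan-Meier by cohort with a confidence interval, events as in Section 11.1.6, censoring at the last adequate tumor assessment, and a stated treatment of unassessable patients. The open wording of the discussion clause is a fair trade-off in an exploratory single-arm study, because the promising label stays tied to response.

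The stopping rule, the success rule and their error rates (0.114, 0.219 and 0.540 recomputed) hold as written. The residual uncertainty is in a descriptive median: one or two progressions' difference for 2 or 4 unassessable patients in 25, and four in the extreme case of 8. This conclusion assumes that the clause is used as worded, as a discussion of possible later work, and that PFS is reported descriptively. It would change if a cohort were declared successful on PFS or stable disease.

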13.1.2.3 Secondary Objective

• To evaluate the pharmacodynamic response to therapy in tumor biopsies (first 15 patients enrolled overall, minimum 4 patients biopsied in each of expansion cohorts 1, 2, and 3)

13.1.2.4 Secondary Endpoints

• Pharmacodynamic Endpoints: Change in levels (between pre-treatment and day 15 tumor biopsies) of proteins/mRNAs implicated in MAPK or BCL2 family signaling, proliferation markers (Ki67), or apoptosis markers (Cleaved caspase-3)

13.2 Sample Size/Accrual Rate

13.2.1 Part 1 (Phase 1b)

Depending on whether enrollment also occurs to the B dosing cohorts for dose levels 1-3, overall accrual to Part 1 of this study will likely be between 21-30 patients. It is estimated that between 3-5 patients will be enrolled per month to the phase 1b portion of the study, resulting in an accrual time of between 6-9 months.

13.2.2 Part 2 (Phase 2)

Part 2 of the study will involve four expansion cohorts each enrolling a maximum of 25 patients. Each cohort will enroll a minimum of 12 patients, and will enroll an additional 13 patients (for 25 total patients) if at least one objective tumor response is observed among the first 12 patients (as described above). Therefore, a minimum of 48 patients and a maximum of 100 patients will be enrolled to this part of the study. Based on past accrual rates at DF/HCC for patients with KRAS or NRAS mutation-positive solid tumors, we estimate that between 8-10 patients will be enrolled per month to the phase 2 portion of the study, resulting in an anticipated maximum accrual time of 10-12 months.

13.2.3 Accrual Targets

Accrual Targets							
Ethnic Category		Sex/Gender					
Ethine Category		Females			Males		Total
Hispanic or Latino	6		+	5	_	11	
Not Hispanic or Latino	61		+	58	_	119	
Ethnic Category: Total of all subjects	67	(A1)	+	63	(B1) =	130	(C1)
Racial Category							
American Indian or Alaskan Native	1		+	1	=	2	
Asian	7		+	6	=	13	
Black or African American	8		+	7	=	15	
Native Hawaiian or other Pacific Islander	2		+	1	=	3	
White	49		+	48	=	97	
Racial Category: Total of all subjects	67	(A2)	+	63	(B2) =	130	(C2)
		(A1 = A2)			(B1 = B2)		(C1 = C2)

13.3 Stratification Factors

N/A

13.4 Analysis of Secondary Endpoints

13.4.1 Secondary Endpoints for Part 1 (Phase 1b)

13.4.1.1 Pharmacokinetic Endpoints

The following pharmacokinetic endpoints will be measured and reported for navitoclax and trametinib.

- Maximum observed plasma drug concentration (Cmax)
- Area-under-the concentration-time-curve from zero (pre-dose) to 24 hours (AUC(0-24)) for trametinib and navitoclax when administered in combination.
- pre-dose (trough) drug concentration at the end of the dosing interval for trametinib and navitoclax when administered in combination.
- t1/2 of trametinib and navitoclax when administered in combination.

In particular, in dose levels 1A and 2A, the Cmax and AUC(0-24) for navitoclax will be assessed pre-trametinib (e.g. day 7 of lead-in dose in Schedule A) and after 2 weeks of trametinib co-administration (day 21 of schedule A, 14th day of trametinib dosing) to determine if any increase or decrease in navitoclax levels are observed following initiation of trametinib (indicative of drug interaction).

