1.2 Secondary Objectives

1.1.3 Part 1 (Phase 1b) Secondary Objectives

To determine the pharmacokinetics of both drugs administered together.

To assess for evidence of response to therapy.

To evaluate the pharmacodynamic response to therapy in tumor biopsies

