Other AEs of interest include elevation in liver enzymes, which has limited some subjects' dosing. As such, liver function tests should be routinely monitored during the conduct of navitoclax studies.

Some investigators have reported QTc prolongation as non serious adverse events (Investigator's Brochure, 2011). Many of these subjects were heavily pretreated with cardiotoxic drugs. Based on nonclinical evaluation, it is unknown or unlikely that QTc prolongation is related to navitoclax administration; however, further clinical QTc investigation is planned. Additionally, metabolic changes such as hyperuricemia, hyperkalemia, and increased lactate dehydrogenase (LDH) values have been reported and are consistent symptoms of tumor lysis syndrome (TLS). One serious adverse event of TLS was reported; however, with continued treatment with prophylaxis, no further events of TLS have been reported. A treatment management strategy for subjects experiencing TLS is discussed in Section 6.

The following recommended phase 2 doses (RP2D) were independently determined based on their respective safety and tolerability results:

- M06-814 (lymphoid malignancies): 7-day lead-in dose of 150 mg/day followed by 325 mg QD (21/21 days) (Wilson *et al.*, 2010).
- M06-822 (SCLC and other solid tumors): 7-day lead-in dose of 150 mg/day followed by 325 mg QD (21/21 days) (Gandhi *et al.*, 2011).
- M06-873 (CLL): 7-day lead-in dose of 100 mg/day followed by 250 mg QD

(21/21 days) (Roberts et al., 2012).

Clinical Pharmacokinetics

Pharmacokinetic (PK) data were obtained for the intermittent (14/21) dosing schedules in trials M06-814, M06-822, and M06-873, and for the continuous (21/21) dosing schedule in trial M06-873. M06-814 also tested for food effects on PK parameters. Overall, the absorption of navitoclax after oral dosing was relatively slow, with C_{max} achieved around 6-9 hours after first dose. Exposure (C_{max} and AUC₀₋₂₄) was approximately dose-proportional over a range of doses from 10 mg/day through 475 mg/day. There were no significant differences in PK values between disease groups (general lymphoid malignancies, SCLC, and CLL) (Investigator's Brochure, 2011). Individual study results are summarized below.

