Trial M06-814: Peak concentration was observed approximately 9 hours after dosing, with a terminal plasma half-life ($t_{1/2}$) of approximately 17 hours, with first-order elimination kinetics (Wilson *et al.*, 2010). Exposure was dose-proportional over a range of 10 mg/day to 440 mg/day, with an interpatient variability in exposure of 40%. The dose-normalized C_{max} and AUC_{0-24} of a non-fasting dose was about 20% higher than a fasting dose among subjects in the 10 mg through 440 mg cohorts. Dosages \geq 315 mg/day met the minimum plasma exposure predicted to be in the therapeutic range based on animal models. After a fasting dose, the oral clearance of navitoclax averaged about 4.4 L/h across all dose levels (Investigator's Brochure, 2011). Navitoclax was not detected in urine, indicating little to no renal excretion.

Trial M06-822: Peak concentration was observed approximately 7 hours after dosing, with a $t_{1/2}$ of approximately 15 hours (Gandhi *et al.*, 2011). Exposure (C_{max} and AUC_{0-24}) was dose-proportional over a range of 10 mg/day to 475 mg/day. Interpatient variability in dose-normalized C_{max} and AUC_{0-24} was about 40%, and values were similar between fasting and non-fasting conditions. Peak-to-trough plasma concentration ratio was close to twofold at steady state. Dosages \geq 225 mg/day met the minimum plasma exposure predicted to be in the therapeutic range based on animal models.

Trial M06-873: Peak concentration was observed approximately 6-8 hours after dosing in both the intermittent and continuous dosing cohorts (Roberts *et al.*, 2012). Exposure was dose-proportional over a range of 10 mg/day to 250 mg/day in the intermittent cohort, and interpatient variability in AUC was 46% for intermittent and continuous cohorts. No consistent trend was observed in dose-normalized steady-state trough concentrations over time. Navitoclax exposure did not demonstrate any correlation with age, sex, body weight, body surface area, renal function, or total bilirubin levels.

Clinical Efficacy

Trial M06-814: Overall, 21 of 46 patients with assessable adenopathy showed some reduction in tumor size (Wilson *et al.*, 2010). Ten of these patients achieved a PR of at

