2.5 Correlative Studies Background

2.5.1 Pharmacokinetic Studies

While the pharmacokinetics of trametinib and navitoclax given as single agents is well-understood, this study will evaluate the pharmacokinetics of these agents when given in combination. During the Phase 1b portion of the study, subjects will have blood drawn pre-dose, and 2h, 4h, 6h, 8h, and 23h after dosing on (1) day 7 of a 7-day navitoclax single-agent lead-in dosing period and (2) again after 14 days of combination dosing. Pre-dose (0h) levels of trametinib and navitoclax will also be measured on day 1 of cycles 2, 4, 8 and 12. Plasma concentrations of trametinib will be determined through established procedures by GSK, and concentrations of navitoclax will be determined through established procedures by AbbVie. These studies will be used to determine whether trametinib and navitoclax interact from a pharmacokinetic standpoint, and will be used to determine the maximum observed plasma drug concentration (Cmax), area-under-the concentration-time-curve from zero (pre-dose) to 24 hours (AUC(0-24)), pre-dose (trough) drug concentration for trametinib and navitoclax, and t1/2. Since it is not yet clear whether the single-agent MTDs of these compounds can reached when these agents are dosed in combination, measuring the plasma drug concentrations achieved at

each dose level provide a valuable comparison of the drug exposure achieved at a given dose level to what is known to be achieved at the single-agent MTD.

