Dose levels 1-3 will be enrolled according to Schedule A (i.e. dosing cohorts 1A, 2A, 3A). After completion of dose level 3A, if dose escalation is warranted per the criteria outlined in Table 5.3 above, an investigator meeting will be held with NCI/CTEP and pharmaceutical collaborators to review safety data. Pharmacokinetic data will be reviewed to evaluate for any evidence of drug interaction, and adverse event data will be reviewed to evaluate for any potentiation of toxicity (in particular, thrombocytopenia) by the combination. If significant safety concerns are noted, dose escalation will proceed for the remainder of the study according to Schedule A (i.e. to dosing cohort 4A, 5A, 6A, 7A). If no significant safety concerns are noted, and it is deemed safe to proceed, dosing will return to dose level 1 according to schedule B (i.e. dosing cohort 1B). Dose escalation will then proceed according to Schedule B to dosing cohort 3B. Since both dose levels 2 and 3 involve beginning with 150 mg navitoclax and 1.5 mg trametinib, it is not necessary to evaluate dose levels 2 and 3 both according to schedule B, as both would test the safety of initiating navitoclax and trametinib simultaneously at these same doses. Therefore, dose escalation will proceed directly from cohort 1B to cohort 3B. If >1 DLT is experienced within dosing cohort 1B or within 3B, then Schedule B will be abandoned, and dose escalation will proceed with dosing cohort 4A. If dosing cohort 3B is completed with ≤1 DLT, then a second investigator meeting will be held with NCI/CTEP and pharmaceutical collaborators to review safety data. Pharmacokinetic data will be reviewed to evaluate for any evidence of drug interaction, and adverse event data will be reviewed to evaluate for any potentiation of toxicity (in particular, thrombocytopenia) by the combination. If the investigators and NCI/CTEP and pharmaceutical collaborators agree that Schedule B demonstrates a comparable or improved safety profile relative to Schedule A, then dose escalation will proceed according to Schedule B (i.e. to dosing cohort 4B, 5B, 6B, 7B) until the RP2D is determined. However, if evidence of drug interaction exists, or if the investigators and NCI/CTEP and pharmaceutical collaborators agree that Schedule A demonstrates a superior safety profile, particularly as it relates to navitoclax-associated thrombocytopenia, then dosing will proceed for the remainder of the study according to Schedule A (i.e. to dosing cohort 4A, 5A, 6A, 7A) until the RP2D is determined. If, however, unacceptable toxicity (either >1 DLT or toxicity not meeting criteria for DLT, but deemed to be unacceptable by investigators) is observed at a given dose level independent of schedule A or B, then and alternative dosing schedule (Schedule C) will be explored with intermittent trametinib dosing (days 1-14 only of each 28 day cycle), beginning at the last dose level completed. With Protocol Version 10 (dated 8/9/16), there will be no further Dose Escalation on Schedule A or B.

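### The PK plan counts any change in navitoclax exposure as a sign of interaction, with no estimate, interval or size to separate interaction from chance variation

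*Combined protocol and SAP*

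**What the plan says.** The formal Part 1 secondary objective (Section 1.1.3) is "To determine the pharmacokinetics of both drugs administered together". Section 2.5.1 adds a yes/no purpose, which Section 9.3.1.1 repeats: "These studies will be used to determine whether trametinib and navitoclax interact from a pharmacokinetic standpoint".

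The only analysis text for that question is in Section 13.4.1.1. It opens descriptively: "The following pharmacokinetic endpoints will be measured and reported for navitoclax and trametinib". It then singles out levels 1A and 2A, where navitoclax Cmax and AUC(0-24) are taken before trametinib (day 7) and "after 2 weeks of trametinib co-administration (day 21 of schedule A, 14th day of trametinib dosing"). The stated aim is "to determine if any increase or decrease in navitoclax levels are observed following initiation of trametinib (indicative of drug interaction". Neither this section nor Sections 2.5.1, 5.1.1, 9.3.1.1 or 13.1.1.4 gives a summary statistic, confidence interval, minimum change or no-effect bounds.

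Section 5.1.1 attached a consequence. After cohort 3B, PK and adverse event data go to a meeting of the investigators, NCI/CTEP and the collaborators. The route to Schedule A then opens "However, if evidence of drug interaction exists", or if the parties agree that Schedule A has the better safety profile. The same section ends by stating that from Protocol Version 10 (8/9/16) there is no further escalation on Schedule A or B.

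**The concern.** Cmax and AUC(0-24) are continuous, so two measurements on different days will differ whether or not trametinib does anything. A criterion met by any difference in either direction carries no information about interaction. What does carry information is how large the average within-patient change is and how precisely it is known, and the plan asks for neither.

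The documents pose a yes/no question, and Section 5.1.1 let the answer send dosing to Schedule A by itself (the condition is joined by an or). Evidence of interaction is not defined anywhere else. At stake now is the reported conclusion. A chance change could be written up as an interaction, or a real one dismissed, and a reader would have no interval by which to judge either.

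**Working it through.** The plan states no sample size, power, margin or alpha for this comparison, so there is no figure to reproduce.

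**Inputs from the documents**
- Patients: 3 per dose level, expanding to 6 after one DLT (Section 5.1.1). Levels 1A and 2A together give 6 to 12.
- Navitoclax is 150 mg at both levels; trametinib is 1 mg in level 1 and 1.5 mg in level 2 (Table 5.1).
- Navitoclax half-life is about 15 to 17 h (Section 2.2.2).
- Variability: "interpatient variability in exposure of 40" per cent in one trial and 46% for AUC in another (Section 2.2.2). These are between-patient figures.

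**Assumptions**
- Within-patient CV of 15% to 40%. The documents give no value.
- Bounds of 0.80-1.25 as an example of a change that matters.

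**Step 1: the literal criterion.** For a continuous paired measurement, P(change is not exactly zero) = 1 for any n, with or without an interaction.

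**Step 2: is the design usable?** When the day 7 dose is taken, 144 h after the first dose, the fraction of steady state is 1 - 0.5^(144/t½). That is 0.997 at 17 h and 0.999 at 15 h. Dose is constant and each patient is their own control, so the day 21/day 7 ratio is a sensible estimate of trametinib's effect.

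**Step 3: how far chance moves the mean ratio.** On the log scale, SE = sqrt(2/n) × sqrt(ln(1 + CV²)). With no interaction, P(geometric mean ratio outside 0.80-1.25) = 2 × [1 - Φ(ln 1.25 / SE)]. The typical 90% CI is the ratio times or divided by exp(t × SE), where t is the 95th percentile on n - 1 degrees of freedom.

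Worked case, CV 25%: sqrt(ln 1.0625) = 0.246.
- n = 6: SE = 0.577 × 0.246 = 0.142. P = 2 × [1 - Φ(0.223/0.142)] = 0.12. CI factor = exp(2.015 × 0.142) = 1.33.
- n = 12: SE = 0.408 × 0.246 = 0.101. P = 0.03. CI factor = exp(1.796 × 0.101) = 1.20.

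| Assumed CV | n=6: P(outside) | n=6: CI factor | n=12: P(outside) | n=12: CI factor |
|---|---|---|---|---|
| 15% | 0.01 | 1.19 | <0.001 | 1.12 |
| 20% | 0.05 | 1.26 | 0.006 | 1.16 |
| 25% | 0.12 | 1.33 | 0.03 | 1.20 |
| 30% | 0.19 | 1.41 | 0.06 | 1.24 |
| 40% | 0.32 | 1.57 | 0.16 | 1.33 |

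Single patients are much noisier. With no interaction, one patient's ratio falls outside 0.80-1.25 with probability 29% (CV 15%) to 68% (CV 40%).

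**Step 4: what an interval could settle.** Over CVs of 15% to 40%:
- If a signal means that the 90% CI excludes 1, it arises by chance in 10% of trials.
- The ratio detectable with 80% power at two-sided 5% is 1.35 to 2.18 at n=6 and 1.21 to 1.62 at n=12.
- With a true ratio of 1, the chance that the 90% CI lies wholly inside 0.80-1.25 is 0.48 down to 0.01 at n=6 and 0.92 down to 0.03 at n=12 (simulation).

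A large interaction can be seen. A modest one usually cannot be ruled out.

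**The case against.** The strongest reply is that the sentence is not a test. The endpoints are to be measured and reported, the formal objective is to describe the PK of both drugs, and Section 5.1.1 has people review PK alongside safety data. This stands against two inferences that a reader might draw. One is that the interaction objective cannot return a valid answer. It can: step 2 shows that the collected data support a valid ratio and interval, and the descriptive objective is unaffected. The other is that the plan runs a test with a 100% false-positive rate. No test, alpha or automatic conclusion is specified, so there is no test to have that rate. What the reply does not supply is any way to get from the day 7 and day 21 values to an answer to the question in Section 2.5.1.

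Four further points also hold:
- The A-versus-B choice is closed. While it was open, a false signal led to Schedule A, which Section 5.1.1 calls the safer initial approach.
- A real effect should not be presumed from Section 8.1.1 calling trametinib a weak CYP3A4 inducer. The same passage does not expect interactions with sensitive 3A4 substrates.
- Restricting the comparison to 1A and 2A is a strength. From level 3 up, a 150 mg lead-in is compared with 200 mg or more. Section 2.2.2 describes exposure only as "approximately dose-proportional over a range of doses from 10 mg/day through 475 mg/day", so any departure from proportionality would be mixed with trametinib's effect.
- Small cohorts limit precision, and wording cannot cure that.

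**Conclusion.** The point holds as a missing criterion and a missing precision statement. As written, Section 13.4.1.1 cannot separate interaction from chance variation, because some change is always observed. By chance alone the geometric mean ratio in 6 patients would leave 0.80-1.25 in 1% to 32% of trials; in 12 patients the figure is under 0.1% to 16%. It is a secondary endpoint and the repair is confined to the analysis text.

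The figures rest on the assumed within-patient CV, on bounds that are not in the documents, and on complete pairs. They also assume trametinib-free days 1-7 in levels 1A and 2A. Section 13.4.1.1 and the Schedule A PK table (9.3.1.2.1) imply this, while Table 5.1 and the text of Section 5.1.1 confine the lead-in to levels 3-7. Those passages must be reconciled, since the day 7 baseline depends on them.

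**What to change.** Replace the sentence in Section 13.4.1.1 with text to this effect:

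- **Estimate.** Report the within-patient geometric mean ratio (day 21/day 7) of navitoclax AUC(0-24) and Cmax with a 90% CI, computed on the log scale. Pool levels 1A and 2A, state the number of pairs (about 6 to 12), and also show each level because the trametinib dose differs.
- **Sensitivity analysis.** Dose-normalised higher Schedule A levels may be added, labelled as sensitivity only and as relying on approximate dose proportionality.
- **Interpretation, in three exclusive outcomes.** (a) The CI excludes 1 and is not wholly within the bounds: evidence of interaction. (b) The CI lies within the bounds, whether or not it excludes 1: no relevant interaction. A CI of 0.85-0.95 falls here. (c) Anything else: inconclusive.
- **Bounds.** State them, for example 0.80-1.25, as a choice, and as post hoc for cohorts already treated.
- **Cross-reference.** Point the phrase on evidence of interaction in Section 5.1.1 to this definition, noting that the A/B decision has been taken.

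The cost is wording and one paired log-ratio analysis of samples already scheduled. The downside is that the answer may often be inconclusive. At an assumed CV of 25% and the typical CI width, outcome (b) is out of reach at n=6, because the ratio would have to be at least 0.80 × 1.33 = 1.06 and at most 1.25/1.33 = 0.94. At n=12 it needs a ratio between 0.80 × 1.20 = 0.96 and 1.25/1.20 = 1.04. The report should say so.
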